12.3 Treatments

The Safety set will be used for the analyses below. Categorical data will be presented as frequencies and percentages. For continuous data, mean, standard deviation, median, 25th and 75th percentiles, minimum, and maximum will be presented.

The duration of exposure in days to ruxolitinib will be summarized by means of descriptive statistics. The dose intensity (computed as the ratio of actual cumulative dose received and actual duration of exposure) for the ruxolitinib arm will be summarized.

The number of subjects with dose adjustments and the reasons will be summarized by group and all dosing data will be listed.

Concomitant medications and significant non-drug therapies prior to and after the start of the study treatment will be listed and summarized according to the Anatomical Therapeutic Chemical (ATC) classification system by group.

12.4 Analysis of the primary endpoint(s)

The primary objective of the proposed study is to evaluate the activity of ruxolitinib added to standard dose corticosteroids +/- CNI in pediatric subjects with moderate or severe treatment naive-cGvHD or SR-cGvHD measured by **Overall Response Rate (ORR)** at Cycle 7 Day 1 based on all subjects in the study. The analysis will be performed based on FAS.

12.4.1 Definition of primary endpoint(s)

The primary efficacy variable of the study is **overall response rate (ORR)** at Cycle 7 Day 1, defined as the proportion of subjects demonstrating a complete response (CR) or partial response (PR), according to the NIH Consensus Criteria ([Lee et al 2015](#)). Note that response is relative to the assessment of cGvHD at baseline.

- **Complete response** is defined as complete resolution of all signs and symptoms of cGvHD in all evaluable organs without initiation of any new systemic therapy.
- **Partial response** is defined as an improvement in at least one organ (e.g. improvement of 1 or more points on a 4 to 7 point scale, or an improvement of 2 or more points on a 10 to 12 point scale) without progression in other organs or sites, or initiation/ addition of new systemic therapies.
- **Lack of response** is defined as unchanged, mixed response, or progression. (Please refer to [Table 8-3](#) and [Table 16-3](#) for the definitions of "unchanged", "mixed response" and "progression".)

cGvHD Flare and **cGvHD Recurrence** are not considered as a treatment failure, unless they require a change or addition of another systemic treatment defined as below.

- **cGvHD Flare** is defined as any increase in symptoms or therapy for cGvHD after an initial response (CR or PR). A cGvHD flare is not considered a treatment failure unless a change or addition of another systemic treatment, including CNIs, occurs.
- **cGvHD Recurrence** is defined as the return of cGvHD disease after tapering off study treatment due to response. Following completion of a taper of systemic therapy, if worsening of cGvHD symptoms occur, the patient is allowed to resume treatment for cGvHD as per local institutional practice. For the statistical analyses, re-start of treatment for cGvHD is handled in the same way as addition or initiation of new systemic treatment.

12.4.2 Statistical model, hypothesis, and method of analysis

The response rates for ORR at Cycle 7 Day 1, will be estimated on the Full Analysis Set (FAS). Confidence intervals of 90% will be calculated based on the exact method for binomial distribution. Summary statistics (frequencies and percentages) will be provided.

12.4.3 Handling of missing values/censoring/discontinuations

Subjects with missing assessments that prevent the evaluation of the primary endpoint will be considered as non-responders. This includes missing cGvHD assessments at baseline and Cycle 7 Day 1.

Subjects who discontinue study treatment should return for the regular assessments indicated in [Section 9.1](#). Addition or initiation of a new systemic therapy before Cycle 7 Day 1 will be considered a treatment failure, and subjects will be counted as non-responder in the primary analysis.

12.4.4 Sensitivity and Supportive analyses

Supportive analysis will include:

- A detailed description of response rates (CR, PR, Unchanged, mixed response and progression) at Cycle 7 Day 1
- A detailed description of the organ-specific response for all organs at Cycle 7 Day 1
- If at least 18 subjects are enrolled with either first line vs. SR-cGvHD respectively, the ORR will be explored for treatment naive and SR subgroup subjects.

12.5 Analysis of secondary endpoints

The secondary objectives in this study include the assessment of: failure free survival (FFS), ORR at Cycle 4 Day 1 (end of Cycle 3), duration of response, overall survival (OS), non-relapse mortality (NRM), best overall response (BOR), cumulative incidence of malignancy relapse/recurrence (MR), reduction and successful tapering of corticosteroid treatment (Cycle 7 Day 1), pharmacokinetics, safety and graft failure.

12.5.1 Secondary efficacy objective(s)

Failure Free Survival

FFS is a composite time to event endpoint incorporating the following FFS events: i) relapse or recurrence of underlying disease or death due to underlying disease, ii.) non-relapse mortality, or iii.) addition or initiation of another systemic therapy for cGvHD.

The FFS distribution will be estimated using the Kaplan-Meier method, and the Kaplan-Meier curves, medians, 3, 6, 12, 18, 24 and 36 month FFS estimates and 95% confidence intervals ([Brookmeyer and Crowley J. 1982](#)) will be presented based on FAS.

The cumulative incidence curve of each of the three FFS components (considering the other two components as a competing risk) as well as estimates at 3, 6, 12, 18, 24 and 36 months will also be presented with 95% confidence intervals.

Best overall response (BOR)

Best overall response (BOR) is defined as proportion of subjects who achieved overall response (CR or PR) at any time point until Cycle 7 Day 1 or the start of additional systemic therapy for cGvHD.

BOR and its 90% confidence interval will be presented based on FAS.

ORR at Cycle 4 Day 1 (end of Cycle 3)

ORR (CR+PR) at Cycle 4 Day 1 and its 90% confidence interval will be presented based FAS.

Duration of Response

Duration of response (DOR) is assessed for responders only. DOR is defined as the time from first response until cGvHD progression, death, or the date of additional systemic therapies for cGvHD. Subjects without event will be censored at the last contact date. Kaplan-Meier method and the Kaplan-Meier curves, medians, 3, 6, 12, 18, 24 and 36 months survival probabilities with 95% confidence intervals will be presented based on FAS.

Overall survival (OS)

The OS distribution will be estimated using the Kaplan-Meier method, and the Kaplan-Meier curves, medians, 3, 6, 12, 24 and 36 month survival probabilities and 95% confidence intervals ([Brookmeyer and Crowley J. 1982](#)) will be presented based on all subjects in the study.

Non-Relapse Mortality (NRM)

Non-relapse mortality (NRM), defined as the time from date of treatment assignment to date of death not preceded by underlying disease relapse/recurrence. Cumulative incidence of NRM and derived probabilities at Months 1, 2, 6, 12, 18, 24 & 36 will be estimated based on all subjects in the study, considering underlying disease relapse/recurrence as competing events.

Incidence of Malignancy Relapse/Recurrence (MR)

The cumulative incidence curve for MR and estimates at 3, 6, 12, 18, 24 and 36 months with 95% confidence intervals will be presented for subjects with underlying hematologic malignant disease, accounting for NRM as the competing risk. In addition, the proportion of subjects who had hematologic malignancy relapse/recurrence and its 95% confidence interval at 3, 6, 12, 18, 24 and 36 months will be presented for subjects with underlying hematologic malignant disease.

Reduction of daily corticosteroid dose

This will be assessed by the proportion of subjects with $\geq 50\%$ reduction from baseline in daily corticosteroid dose at Cycle 7 Day 1, based on all subjects enrolled in the study.

A sensitivity analysis of the same endpoint, to exclude dose interruption of corticosteroids due to AE, might be planned in the Statistical Analysis Plan (SAP) per the alignment across the REACH studies.

Reduction to low dose corticosteroids

This will be assessed by the proportion of subjects with reduction from baseline in daily corticosteroid dose to methylprednisolone-equivalent steroid dose of $\leq 0.2\text{mg/kg/day}$ (or equivalent dose of $\leq 0.25\text{mg/kg/day}$ prednisone or prednisolone) at Cycle 7 Day 1, based on all subjects enrolled in the study.

A sensitivity analysis of the same endpoint, to exclude dose interruption of corticosteroids due to AE, might be planned in the SAP per the alignment across the REACH studies.

Graft Failure

This will be assessed by donor cell chimerism, defined as initial whole blood or marrow donor chimerism for those who had $\geq 5\%$ donor cell chimerism at baseline. If donor cell chimerism declines to $< 5\%$ on subsequent measurements, graft failure is declared. The percentage of graft failure with 95% confidence intervals at 3, 6, 12, 18, 24 and 36 months will be presented. Case descriptions will be used in case of very few subjects with graft failure (e.g. less than 5 subjects).

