Study completion	Point/time at which the subject came in for a final evaluation visit or when study drug (ruxolitinib) was discontinued whichever is later.
Study drug discontinuation	Point/time when subject permanently stops taking study drug (ruxolitinib) for any reason; may or may not also be the point/time of premature subject withdrawal.
Study treatment	Any single drug or combination of drugs or intervention administered to the subject as part of the required study procedures.
Subject	A trial participant (can be a healthy volunteer or a patient).
Subject number	A unique number assigned to each subject upon signing the informed consent. This number is the definitive, unique identifier for the subject and should be used to identify the subject throughout the study for all data collected, sample labels, etc.
Variable	A measured value or assessed response that is determined from specific assessments and used in data analysis to evaluate the drug being tested in the study.
Withdrawal of consent (WoC)/ Opposition to use data/biological samples	Withdrawal of consent from the study occurs when the patient explicitly requests to stop use of their data and biological samples (opposition to use data and biological samples) AND no longer wishes to receive study treatment AND does not agree to further required assessments. This request should be in writing (depending on local regulations) and recorded in the source documentation. Opposition to use data/biological samples occurs in the countries where collection and processing of personal data is justified by a different legal reason than consent.

Amendment 2

As of 17-Sept-2021, CINC424G12201 enrollment was completed with a total of 46 subjects enrolled, which included 22 subjects in Group 1 (age ≥ 12 y to < 18 y), 17 subjects in Group 2 (age ≥ 6 y to < 12 y) and 7 subjects in Group 3 (age ≥ 2 y to < 6 y).

The main purpose of amendment 2 is to include public health emergency disruption proofing language, to add one exploratory objective regarding corticosteroid-free response rates, to provide clarification on ruxolitinib treatment management and to clarify subject withdrawal of consent.

Changes to the protocol

Changes to specific sections of the protocol are shown in the track changes version of the protocol using strike through red font for deletions and red underline for insertions. The following sections of the protocol have been changed:

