12.8 Sample size calculation

12.8.1 Primary endpoint(s)

The sample size for the primary objective of measuring ORR at Cycle 7 Day 1 is approximately 42 subjects, regardless of age.

The sample size calculation is based on the ORR at Cycle 7 Day 1, and the calculation will consider the Saw-Toothed behavior of power waving for single binomial proportion using an exact method ([Chernick and Liu 2002 ; Published online: 01 Jan 2012](#)). Considering the response rate of children using corticosteroids is 30% to 50% ([Wolff et al 2011](#)), we assume the true ORR at Cycle 7 Day 1 of the study population is 70%, and therefore, a minimum sample size of 42 subjects would provide >80% probability to have a 90% CI with lower limit $\geq 50\%$. [Table 12-1](#) provides estimates of the probability to have a 90% CI with lower limit $\geq 50\%$, minimum number of responders required and two-sided 90% Clopper-Pearson CIs for various sample sizes.

Table 12-1 Probability to have a 90% CI with lower limit $\geq 50\%$ and 90% confidence intervals for different number of subjects

Sample size	Minimum No. of responders	Response Rate	Probability to have a 90% CI with lower limit $\geq 50\%$	90% CI	
30	20	0.67	0.730	0.501	0.807
31	21	0.68	0.688	0.515	0.813
32	22	0.69	0.644	0.528	0.820

Sample size	Minimum No. of responders	Response Rate	Probability to have a 90% CI with lower limit $\geq 50\%$	90% CI	
33	22	0.67	0.733	0.509	0.801
34	23	0.68	0.693	0.522	0.807
35	23	0.66	0.773	0.504	0.789
36	24	0.67	0.737	0.517	0.795
37	24	0.65	0.807	0.500	0.778
38	25	0.66	0.774	0.512	0.784
39	26	0.67	0.740	0.523	0.790
40	26	0.65	0.807	0.508	0.774
41	27	0.66	0.776	0.519	0.780
42	27	0.64	0.836	0.505	0.765
43	28	0.65	0.808	0.515	0.771
44	28	0.64	0.861	0.501	0.757
45	29	0.64	0.836	0.511	0.763
46	30	0.65	0.809	0.521	0.768
47	30	0.64	0.860	0.508	0.755
48	31	0.65	0.836	0.517	0.760
49	31	0.63	0.881	0.505	0.747
50	32	0.64	0.859	0.514	0.753

13 Ethical considerations and administrative procedures

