The proportion of subjects with $\geq 50\%$ reduction from baseline in daily corticosteroid dose due to disease improvement at Cycle 7 Day 1, and its 95% confidence interval will be presented based on all subjects in the FAS. For the final CSR the analyses will be done considering data up to end of study.

Reduction to low dose corticosteroids

The proportion of subjects with reduction from baseline in daily corticosteroid dose to methylprednisolone-equivalent steroid dose of $\leq 0.2\text{mg/kg/day}$ (or equivalent dose of $\leq 0.25\text{mg/kg/day}$ prednisone or prednisolone) due to disease improvement at Cycle 7 Day 1, and its 95% confidence interval will be presented based on all subjects in the FAS. For the final CSR the analyses will be done considering data up to end of study.

Graft Failure

The percentage of graft failure with 95% confidence intervals at 3, 6, 12, 18, 24 and 36 months will be presented based on all subjects in the FAS. In case of very few patients with graft failure (e.g. less than 5 patients), case descriptions using listings will be provided instead.

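### With few graft failures, SAP 2.7.2 replaces the planned percentage and 95% interval with listings, so this secondary endpoint can lose its only planned interval when an upper bound is most useful

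*Protocol*

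**What the plan says.** Graft failure is a secondary objective in protocol Table 2-1, and SAP Table 1-1 keeps it in the final CSR. An event is a fall in donor chimerism from at least 5% at baseline to below 5%.

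Protocol 12.5.1 sets the analysis: "The percentage of graft failure with 95% confidence intervals at 3, 6, 12, 18, 24 and 36 months will be presented". It then adds: "Case descriptions will be used in case of very few subjects with graft failure (e.g. less than 5 subjects"). That sentence does not say whether the case descriptions replace the percentage or accompany it.

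SAP 2.7.2 repeats the percentage and interval for the FAS and settles the question: "In case of very few patients with graft failure (e.g. less than 5 patients), case descriptions using listings will be provided instead".

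Both documents give the figure of 5 as an example. Neither states an expected graft-failure rate or a confidence-interval method for this endpoint. SAP 2.7.2 takes all FAS subjects as the base, while the definitions in protocol 12.5.1 and SAP 2.7.1 refer to children with at least 5% donor chimerism at baseline. The protocol's Amendment 2 summary reports that "enrollment was completed with a total of 46 subjects enrolled".

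**The concern.** For an uncommon harm in a single-arm trial, the most informative figure is often the upper confidence limit. It is informative even with no events, because it says how large a risk the data can exclude. The SAP rule removes that limit when counts are lowest.

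The cut-off is also discretionary. Treatment is open to the sponsor's trial team (protocol 6.4), so the choice between an estimate and a listing would be made with the count in view. One SAP serves both reports (SAP 2.14), yet the rule does not say whether the count is taken per time point or overall, or at the interim or the final report.

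Malignancy relapse, another secondary endpoint, gets a cumulative incidence and a proportion with 95% intervals at the same six time points and no minimum count (SAP 2.7.2). No reason is given for treating graft failure differently.

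**Working it through.** **The plan's own figure.** The documents give no figure for graft failure. Their only design figure is for the primary endpoint, and it serves here to check the exact-binomial method. Protocol 12.8.1 states that "we assume the true ORR at Cycle 7 Day 1 of the study population is 70"%, and Table 12-1 gives 0.836 for 42 subjects and at least 27 responders. P(X ≥ 27 | 42, 0.70) = 0.8360, and the 90% Clopper-Pearson limits for 27/42 are 0.5045 and 0.7653, against 0.505 and 0.765 in the table. The row for 46 also agrees (0.8090 against 0.809).

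**Inputs for graft failure.** n = 46 enrolled is a ceiling. The FAS excludes subjects with certain protocol deviations (SAP Table 2-3), and the baseline-chimerism condition could lower n further. The planned size of 42 is used to show the effect of a smaller denominator. The exact method is my choice, since none is named. The calculation treats the 36-month result as one crude proportion with every child's outcome known.

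**Intervals lost if the example cut-off is applied.** For x events in n, lower limit = Beta(0.025; x, n−x+1), or 0 when x = 0. Upper limit = Beta(0.975; x+1, n−x). For x = 0 the upper limit reduces to 1 − 0.025^(1/n), which is 1 − 0.025^(1/46) = 7.7%.

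| Failures | Percentage, n = 46 | Exact 95% CI, n = 46 | Upper limit, n = 42 |
|---|---|---|---|
| 0 | 0% | 0 to 7.7% | 8.4% |
| 1 | 2.2% | 0.1 to 11.5% | 12.6% |
| 2 | 4.3% | 0.5 to 14.8% | 16.2% |
| 3 | 6.5% | 1.4 to 17.9% | 19.5% |
| 4 | 8.7% | 2.4 to 20.8% | 22.6% |

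The smallest result that would still get its planned interval under the example is 5/46 = 10.9% (3.6 to 23.6%).

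**How often the listing branch would apply.** P(X ≤ 4 | 46, p), over an assumed range of true 36-month risk p:

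| p | 1% | 2% | 3% | 5% | 8% | 10% | 15% | 20% |
|---|---|---|---|---|---|---|---|---|
| P(X ≤ 4) | 99.99% | 99.8% | 98.8% | 92.1% | 69.4% | 50.7% | 16.0% | 3.3% |

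The probability crosses one half at p = 10.1% for n = 46 and at 11.0% for n = 42.

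**Do the adverse-event tables fill the gap?** Protocol 8.3.2 requires graft failure to be recorded as an adverse event too, and SAP 2.8.1 tabulates adverse events by count and percentage with no minimum. Those tables carry no interval and stop 30 days after the last dose (SAP 2.1.1). Children who stop ruxolitinib early are assessed for graft failure every 6 months until 3 years from first dose (protocol 9.1.1). The disclosure tables in SAP 2.8.1.1 cover post-treatment events separately, again with no interval planned.

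**The case against.** The strongest reply is that little is hidden. Every case is described, on-treatment cases are tabulated as adverse events, analysis-set sizes are reported, and a reader could compute a crude interval. No hypothesis is tested, and the SAP uses a similar under-5, listing-only convention for recurrence of chronic GvHD after taper (SAP 2.13). This stands as a reason to rate the point as minor. It does not justify leaving the reader to derive the interval for a stated secondary endpoint; the recurrence analysis is exploratory.

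Some stronger readings are tempting, and the documents do not support them:

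- **That the estimate is dropped whenever fewer than 5 children fail.** Both documents present 5 as an example, and the protocol sentence alone does not say the estimate is dropped. Only the SAP does.
- **That small counts get no percentage at all.** On-treatment cases get one in the adverse-event tables.
- **That suppression is the likeliest outcome.** Protocol 5.1 requires a successful transplant, which makes a low risk plausible, but no rate is given.
- **That any reported estimate is biased upward.** This is true only conditionally on reporting, and its size depends on the risk. At a true 5% and n = 46 the mean reported value would be 11.9%, but a report would occur in only about 8% of trials (100% − 92.1%). At 20% the excess is 0.4 percentage points, and at 30% it is practically nil. Low counts are still disclosed case by case, so a reader sees the count either way.

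**Conclusion.** The point holds in a narrow form and is a low-cost improvement. Under SAP 2.7.2, a judgement on the observed count decides whether graft failure gets its planned percentage and interval. If the example cut-off is used, 0 to 4 failures leave the endpoint with no planned interval, while the data would support exact 95% upper limits of about 7.7% to 20.8% at n = 46, slightly higher with fewer children in the denominator. The adverse-event tables recover the on-treatment count and percentage. They do not recover the interval or most of the post-treatment follow-up to 36 months.

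Two assumptions matter. The listing branch is the more probable one only if the true risk is below about 10% (n = 46) or 11% (n = 42). The limits treat each child's outcome as known; the documents give no rule for counting deaths or losses to follow-up in this endpoint. The primary analysis is unaffected.

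**What to change.** - In SAP 2.7.2, change *instead* to *in addition*. The count, denominator and percentage with an exact 95% interval are then always reported, including for zero events, and case descriptions are added when events are few.
- In protocol 12.5.1, clarify that the case descriptions supplement the estimate.
- State whether the denominator is the FAS or the children with at least 5% donor chimerism at baseline.

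The cost is a small wording change and one table row, with no new data. If the database is already locked, the row can be added to the CSR and labelled as a change to the planned analysis.

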12.5.2 Safety endpoints

For all safety analyses, the safety analysis set will be used. All listings and tables will be presented by group.

The overall observation period will be divided into three mutually exclusive segments:

1. Pre-treatment period: from day of patient's informed consent to the day before first dose of study medication.

2. On-treatment period: from day of first dose of ruxolitinib to 30 days after date of last actual administration of assigned treatment.
3. Post-treatment period: starting at Day 31 after last dose of study medication.

For safety evaluations (except for AE), the last available assessment on or before the date of start of study treatment is taken as the “baseline” assessment.

Safety summaries (tables, figures) include only data from the on-treatment period with the exception of baseline data which will also be summarized where appropriate (e.g. change from baseline summaries). In addition, a separate summary for death including on treatment and post treatment deaths will be provided. In particular, summary tables for (AEs) will summarize only on-treatment events, with a start date during the on-treatment period (*treatment-emergent* AEs).

